2.0 Objectives*

2.1 *Describe the purpose, specific aims, or objectives of this research.*

Aim 1: To determine the feasibility and acceptability of the MMPH in community-dwelling URM adults with PH as a symptom self-management tool.

Aim 1a: Feasibility will be assessed by 1) frequency of home practice (> 2/week) and 2) retention rate (>70% of participants remaining at study completion).

Aim 1b: Acceptability will be determined by 1) participants' evaluation of the MMPH program (composite mean System Usability Scale score > 5, scale 1-7), 2) session completion rate (at least 6 of 8 [75% attendance] by the participants retained at the study end), and 3) qualitative thematic analysis of participants.

Aim 2: To determine the clinical impacts of an MMPH program in PH-symptom, anxiety, and depression reduction among community-dwelling URM adults with PH for symptom management.

2.2 *State the hypotheses to be tested, if applicable.*

NOTE: A hypothesis is a specific, testable prediction about what you expect to happen in your study that corresponds with your above listed objectives.

Hypothesis 1: MMPH will meet feasibility and acceptability targets for URM adults with PH

Hypothesis 2: Participants will report reductions in symptom severity of pain, anxiety, dyspnea, and fatigue at the end of the MMPH modules (short-term impacts). Participants will report decreases in the prevalence and intensity of PH-related symptoms, depression, and improved quality of life at the end of the MMPH program (long-term impacts).

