5.0 Study Design*

5.1 *Describe and explain the study design (e.g. case-control, cross-sectional, ethnographic, experimental, interventional, longitudinal, observational).*

This study will engage community-dwelling URM adults with PH living in the United States. We will use a two-group comparative study design where waitlisted participants will serve as controls. Considering a 20% attrition rate in a behavioral health intervention study, we aim to enroll a total of 20, with at least 16 participants to address study aims (8-10 in each Group).³⁴ As a pilot study, power analysis is not necessary. Statistical analysis will include descriptive statistics, mixed-effect modeling for repeated measures, and within-group and between-groups comparisons using t-tests or Wilcoxon signed-rank test as appropriate and Cohen's d effect size calculation. Multi-time data collection will be done via daily mobile-APP use.

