12.0 Procedures Involved*

12.1 Provide a description of **all research procedures or activities** being performed and when they are performed once a subject is screened and determined to be eligible. Provide as much detail as possible.

NOTE: This should serve as a blueprint for your study and include enough detail so that another investigator could pick up your protocol and replicate the research. For studies that have multiple or complex visits or procedures, consider the addition of a schedule of events table in in your response.

Table 1. Study Procedure

| Procedure | w0-w1 MMPH-1 (Zoom #1) | w1- w2 MMPH-2 (video) | w2-w3 MMPH-3 (video) | w3-w4 MMPH-4 (Zoom #2) | w4- w5 MMPH-5 (video) | w5-w6 MMPH-6 (video) | w6- w7 MMPH-7 (video) | w7-w8 MMPH-8 (video) Zoom #3 |
|------------------------------------|------------------------------|--------------------------------|----------------------------|------------------------------|--------------------------------|----------------------------|--------------------------------|---------------------------------------|
| Instructor-led (min X day) | 60 X 1 | 60 X 1 | 60 X 1 | 60 X 1 | 60 X 1 | 60 X 1 | 60 X 1 | 60 X 1 |
| Self-guided (min X day) | 20 X 6 | 20 X 6 | 20 X 6 | 20 X 6 | 20 X 6 | 20 X 6 | 20 X 6 | 20 X 6 |
| Consent | X | | | | | | | |
| Demographics | X | | | | | | | |
| PAHSS | X | | | X | | | | X |
| EmPHasis-10 | X | | | X | | | | X |
| PHQ-9 | X | | | X | | | | X |
| CAMS-R | X | | | X | | | | X |
| Pain (1-10) | X* | X* | X* | X* | X* | X* | X* | X* |
| Anxiety (1-10) | X* | X* | X* | X* | X* | X* | X* | X* |
| Fatigue (1-10) | X* | X* | X* | X* | X* | X* | X* | X* |
| Dyspnea (1-10) | X* | X* | X* | X* | X* | X* | X* | X* |
| SUS-modified MMPH | | | | | | | | X |
| Interview -MMPH | | | | | | | | X |
| Reminder (via phone or App) - MMPH | X | X | X | X | X | X | X | X |

Note: X* = symptom assessment before and after daily use of MMPH module; PAHSS, Pulmonary Arterial Hypertension Symptoms Scale; EmPHasis-10, Health-related quality of life in pulmonary arterial hypertension; PHQ-9, Patient Health Questionnaire; CAMS-R, Cognitive and Affective Mindfulness Scale-Revised; SUS, System Usability Scale; MMPH, Mindfulness Meditation for Pulmonary Hypertension.

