13.0 Study Timelines*

13.1 *Describe the anticipated duration needed to enroll all study subjects.*

As previously described, we anticipate enrolling all 20 subjects within three months.

13.2 *Describe the duration of an individual subject's participation in the study. Include the length of study visits and overall study follow-up time.*

The duration of an individual subject's participation in the entire study (consent to the completion of focused-group interview) will be three months or less. There will be no physical study visits, only virtual study visits for Zoom participation and individual interview sessions.

- Enrollment, consenting, baseline data = 30 minutes
- Completion of all 8 sessions (60 min/each) = 480 minutes for the 8 weeks
- 20min/day practice for 8 weeks = 56 days X 20 min = 1,120 min = 18.7 hours over 8 weeks = 2.3 hours per week.
- Focused interview = 1 hour
- Questionnaires completion = 10 min X 8 weeks = 80 min total

13.3 *Describe the estimated duration for the investigators to complete this study (i.e. all data is collected and all analyses have been completed).*

The estimated duration for the investigators to complete this study will be about 12 months (recruitment, enrollment, intervention, data collection, data analysis).

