19.0 Data Management and Analysis*

19.1 Describe the data analysis plan, including any statistical procedures. This section applies to both quantitative and qualitative analysis.

As a pilot study, power analysis is not necessary. Statistical analysis will include descriptive statistics, mixed-effect modeling for repeated measures, and within-group and between-groups comparisons using t-tests or Wilcoxon signed-rank test as appropriate and Cohen's d effect size calculation. Multi-time data collection will be done via daily mobile-APP use.

We will follow the standard procedure in quantitative data analysis that includes general data inspection to verify the accuracy, completeness, and normality of the dataset using the SPSS23 program. We will compare clinical outcomes within-group (pre-post) as well as between groups in the post-intervention period. We will follow the recommendation of inappropriate statistical analysis and interpretation specific to each survey. For continuous variables, we will use a paired student t-test, independent t-test analytical approaches. For categorical variables and non-normally distributed variables, we will use non-parametric statistical methods (X2). Frequency distributions will be produced for all variables, and demographic information will be used to describe the sample. The impact of the M-App use on outcome variables will be analyzed using paired t-test and repeated measure ANOVA.

Qualitative data (focused-group interview data) will be analyzed using the standard qualitative thematic analysis procedure. We will transcribe the audio-recorded data and upload it into NViVo data management system. We will adhere to the thematic analysis method, described as follows:

1. A researcher will read and re-read the entire text to get a general sense of the participants' whole experience of being a student during the COVID-19 pandemic. While reading through the transcript, the researcher will take initial notes and perform a general review to get familiar with the data before analyzing the data.
2. The researcher will descriptively open code by dividing the significant text segments into 'meaningful units', keeping the participants' own words. The researcher will re-read all the codes again to eliminate redundancies.

The comparative discussion of these codes with other research team members to achieve a consensus will provide a validation step.

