22.0 Withdrawal of Subjects*

N/A: This study is not enrolling subjects. This section does not apply.

22.1 Describe anticipated circumstances under which subjects may be withdrawn from the research without their consent.

Participants may be withdrawn from the research without their consent if the PI or research team member discovers a participant is in severe psychological distress or is admitted into the hospital for a psychiatric condition.

22.2 Describe any procedures for orderly termination.

NOTE: Examples may include return of study drug, exit interview with clinician. Include whether additional follow up is recommended for safety reasons for physical or emotional health.

NOT APPLICABLE

22.3 Describe procedures that will be followed when subjects withdraw from the research, including retention of already collected data, and partial withdrawal from procedures with continued data collection, as applicable.

We will attempt to use all the available data obtained from all participants (intention to treat). Pre and post comparison of the experimental Group will be conducted as aggregate means using all available data collected.

When participants decide to leave the study, we will ask them if they would allow us to use the data we have collected before their decision to withdraw. If the subjects agree to use the data, the collected data will be handled and analyzed the same as research data. If the participants do not allow the use of the data, we will make every attempt to destroy the data.

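### Section 19.1 names a paired t-test and repeated-measures ANOVA for App use but gives no unit of analysis; the mixed model it already lists should be assigned to these data

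*Combined protocol and SAP*

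**What the plan says.** Section 19.1 has one sentence on the App: "The impact of the M-App use on outcome variables will be analyzed using paired t-test and repeated measure ANOVA". It does not say which outcomes are meant, or whether a pair is a session, a person-week or a person.

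Earlier in the same section, and in 5.1, a general list appears: "Statistical analysis will include descriptive statistics, mixed-effect modeling for repeated measures, and within-group and between-groups comparisons using t-tests or Wilcoxon signed-rank test". The next sentence in both places is "Multi-time data collection will be done via daily mobile-APP use". The mixed model is not tied to any outcome.

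The note to Table 1 (section 12.1) defines the schedule for pain, anxiety, fatigue and dyspnea: "X* = symptom assessment before and after daily use of MMPH module". These ratings run through all eight weeks and are the data for the short-term half of Hypothesis 2 (section 2.2). PAHSS, EmPHasis-10, PHQ-9 and CAMS-R are collected three times, at about weeks 0, 4 and 8.

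The number of sessions per person is not fixed:
- Table 1 gives six self-guided days a week for eight weeks.
- Section 13.2 gives "20min/day practice for 8 weeks = 56 days X 20 min = 1,120 min = 18.7 hours over 8 weeks".
- Section 2.1 accepts practice just above twice a week as feasible.
- Section 4.1 presents mobile delivery as started by the user when wanted.

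On incomplete data, section 22.3 says: "We will attempt to use all the available data obtained from all participants (intention to treat". It adds that the experimental group's pre-post comparison will use aggregate means, without saying at what level the means are taken.

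**The concern.** The only sentence about App impact names two methods that do not suit many unequal sessions per person. A paired t-test over all before/after pairs treats one person's sessions as independent. Repeated-measures ANOVA needs the same complete set of occasions from everyone, which sets it against 22.3. The suitable method is listed nearby but not assigned, so two analysts following 19.1 could run quite different tests on the same ratings. At stake is the short-term claim in Hypothesis 2. It could rest on standard errors that are too small or on a reduced set of completers.

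**Working it through.** **1. The plan's own figure.** Section 5.1 enrols 20 to keep at least 16 after 20% attrition: 16 / (1 − 0.20) = 20. This reproduces. Section 7.3 uses 15% instead: 16 / 0.85 = 18.8, so 19.

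**2. Sessions per person over eight weeks.** Table 1: 6 × 8 = 48. Section 13.2: 56. Feasibility threshold: 2 × 8 = 16, to be exceeded. A range of 16 to 56 is used below.

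**3. Paired t-test if sessions were pooled.** With m sessions per person and within-person correlation of change ρ, the variance of the pooled mean is inflated by

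design effect = 1 + ρ × (Σm² / Σm − 1),

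and the naive standard error is too small by its square root. For m uniform on 16 to 56, the mean is 36 and the variance (41² − 1)/12 = 140, so Σm²/Σm is about (36² + 140)/36 = 39.9. At ρ = 0.3 the design effect is about 1 + 0.3 × 38.9 = 12.7. The documents give no ρ, so it is assumed and shown as a range. Simulated trials with no true effect (4,000 per row, two-sided 0.05) gave:

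| ρ (assumed) | Design effect, 16 people | SE too small by | Pooled test, 16 people | Pooled test, 8 people | Test on person means, 16 / 8 people |
|---|---|---|---|---|---|
| 0.05 | 2.93 | 1.71 | 25.6% | 26.6% | 4.5% / 5.2% |
| 0.1 | 4.87 | 2.21 | 36.6% | 37.2% | 4.8% / 5.2% |
| 0.2 | 8.73 | 2.95 | 50.5% | 50.9% | 4.4% / 4.8% |
| 0.3 | 12.62 | 3.55 | 58.1% | 58.1% | 4.8% / 5.6% |
| 0.5 | 20.36 | 4.51 | 67.0% | 67.9% | 4.9% / 4.6% |

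The number of people hardly changes the pooled error rate. One mean change per person brings it back to about 5%.

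**4. Repeated-measures ANOVA: who remains.** The answer depends on what counts as an occasion, which the plan does not say.

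- *Every session a level.* Expected complete cases of 16 are 16 × q^k, with q the assumed chance of doing each of k sessions, taken as independent.

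| q (assumed) | k = 48 | k = 56 |
|---|---|---|
| 0.80 | below 0.001 | below 0.001 |
| 0.90 | 0.10 | 0.04 |
| 0.95 | 1.4 | 0.9 |
| 0.98 | 6.1 | 5.2 |

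- *Weekly means as levels.* At least one session is needed in each of eight weeks: 16 × [1 − (1 − q)^7]^8. At 2 sessions a week (q = 2/7) this gives 7.2; at 3 a week, 13.6; at 3.5 a week, 15.0.
- *Three questionnaire visits as levels.* 20 × 0.80 = 16 complete and 4 dropped. At 15% attrition, 17 remain.

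**The case against.** The strongest reply is that no section says sessions will be pooled. The App sentence speaks only of outcome variables, and the endpoints in section 3.1 are PAHSS and EmPHasis-10, each measured three times. Section 19.1 also describes within-group comparison as pre-post. On that reading there is one pair per person, a baseline-to-week-8 paired t-test is ordinary, and no standard error is understated. The mixed model is listed directly before the sentence on daily App data, so it may be meant for those data. The study is a pilot of feasibility and preliminary impact, and the module ratings are not among its stated endpoints.

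Much of this stands. A reader might infer that the planned analysis is simply wrong and will give falsely precise results. The documents do not support that: the false-positive rates above belong to one possible reading, and the correlations behind them are assumptions. A reader might also infer that the ANOVA would have almost no complete cases. That holds only if each session is a level and completion is about 95% or lower; it fails for the three-visit scales and for weekly means at three or more sessions a week.

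What the reply does not remove is the ambiguity. The one sentence that mentions App impact names other methods than the mixed model, and nothing excludes pooling. Required fields and call-backs (19.3) can recover a missed entry but not a session that never took place. Even on the mildest reading, a complete-case ANOVA drops people whose data 22.3 says will be used.

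**Conclusion.** The point holds as an unassigned method and an undefined unit of analysis, not as a demonstrated error. Depending on how 19.1 is read, the test of before/after-module change has a false-positive rate near 5% (person means) or between about 26% and 67% (pooled sessions, 16 people, 16 to 56 sessions, assumed correlation 0.05 to 0.5). The ANOVA keeps anything from almost nobody to about 16 of 20. The conflict with 22.3 needs no assumed correlation: at the stated 20% attrition, about 4 of 20 would be left out of the three-visit analysis. The completion rates behind the session-level and weekly counts are also assumptions. This is a free improvement, held with medium confidence.

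**What to change.** Replace the App sentence in 19.1 with wording such as:

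> Ratings of pain, anxiety, fatigue and dyspnea before and after each module will be analysed with a linear mixed model of the session change, with a random intercept for participant and small-sample degrees of freedom (Satterthwaite or Kenward–Roger). All completed sessions are included; sessions not done are not imputed. As a check, each participant's mean change is tested once, with n equal to the number of participants. PAHSS, EmPHasis-10, PHQ-9 and CAMS-R at the three visits will be analysed with the mixed-effects model already named in this section, in place of repeated-measures ANOVA, using every available visit.

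The check matters because the mixed model gives frequent users somewhat more weight, while the test on means weights people equally; a marked difference between the two should be reported.

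Section 22.3 should say at what level its aggregate means are taken. The 48 and 56 practice days (Table 1, 13.2) and the 20% and 15% attrition (5.1, 7.3) should also be reconciled.

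The cost is wording only: the mixed model is already in the plan, and no data, procedures or participants are added.

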18.0 Provisions to Protect the Privacy Interests of Subjects

18.1 Describe how you will protect subjects' privacy interests during the course of this research.

NOTE: Privacy refers to an individual's right to control access to him or herself. Privacy applies to the person. Confidentiality refers to how data collected about individuals for the research will be protected by the researcher from release. Confidentiality applies to the data.

Examples of appropriate responses include: "participant only meets with a study coordinator in a classroom setting where no one can overhear", or "the participant is reminded that they are free to refuse to answer any questions that they do not feel comfortable answering."

To protect participants' privacy interests and safety during the study, a research team member will only contact the participants on the phone in a private office where no one can overhear the conversation. Any email communications with participants will be kept private and confidential. All data collected during the study will be stored on a secure, password-protected cloud that only the research team has access to.

About Zoom communication, participants will meet with a study coordinator from the privacy of their home where no one can overhear the discussion about their participation in the study. Participants will be reminded not to discuss any personal information outside of the group discussion during the Zoom intervention.

The participant will be reminded that they are free to refuse to answer any questions that they do not feel comfortable answering.

18.2 Indicate how the research team is permitted to access any sources of information about the subjects.

*NOTE: Examples of appropriate responses include: school permission for review of records, consent of the subject, HIPAA waiver. This question **does apply** to records reviews.*

Sources of information about the subjects before enrollment will only be accessible to PH doctors. Once enrolled, research data will be stored in Research Files at UBSON, and only research team members (PI, co-I, RA) will have access. There will be no need for medical record review because the outcome data will be participant-reported outcomes (symptom presence, symptom severity, quality of life).

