3. The researcher will use an inductive approach to look over the consensus codes, identify patterns among them, and start coming up with categories that describe 'critical moments,' significant aspects of the experiences.

4. The researcher will categorize the codes into overarching elements and higher-level categories and then cluster similar categories into the related themes. To make sure that the themes are useful and accurately represent the data, the researcher will return to the original data set and reflectively compare the categories against it.

5. The researcher will discuss with the research team members to refine the themes and develop the central theme. The researcher will then define and name the central theme by formulating its meanings and figuring out how it helps understand participants' experiences.

6. Finally, the researcher will develop an overall description of the essence of the participants' experience by merging the themes into the central theme/s in a flowing narration.

19.2 *If applicable, provide a power analysis.*

NOTE: This may not apply to certain types of studies, including chart/records reviews, survey studies, or observational studies. This question is asked to elicit whether the investigator has an adequate sample size to achieve the study objectives and justify a conclusion.

NOT APPLICABLE

19.3 *Describe any procedures that will be used for quality control of collected data.*

We will set up the required data entry field within the M-App and REDCap function to ensure that the data entry is accurate and complete. Erroneous (out-of-range) data entry will be less likely, as controlled by the proper setup of the data fields. Also, the system will remind participants to enter data into the required data field before proceeding to the following sections. A dedicated research coordinator will review data entry once a week to verify survey completion and confirm no missing data. In the case of missing data discovery, the research coordinator will contact and ask participants to complete it as soon as possible.

Before the data analysis process, two researchers will review the dataset for accuracy and discuss any possible reliability issues in data collection.

20.0 **Confidentiality***

A. Confidentiality of Study Data

Describe the local procedures for maintenance of confidentiality of study data and any records that will be reviewed for data collection.

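### Section 19.3's chase rule lets momentary App ratings be completed late and unmarked, which could bias the short-term change by an unknown amount in an unknown direction

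*Combined protocol and SAP*

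**What the plan says.** Section 19.3 treats the two data-capture systems together. It begins: "We will set up the required data entry field within the M-App and REDCap function to ensure that the data entry is accurate and complete". Within a form, "the system will remind participants to enter data into the required data field before proceeding to the following sections". The check on what is still missing is periodic: "A dedicated research coordinator will review data entry once a week to verify survey completion and confirm no missing data". The remedy for a gap is: "In the case of missing data discovery, the research coordinator will contact and ask participants to complete it as soon as possible". Two researchers will also look over the dataset for accuracy and reliability before analysis.

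The note to Table 1 (section 12.1) defines the timing of the four 1-10 symptom items: "X* = symptom assessment before and after daily use of MMPH module". Hypothesis 2 (section 2.2) uses these four symptoms for the short-term impact, at the end of the modules. Section 19.1 assigns the impact of App use to a paired t-test and repeated-measures ANOVA, and it also names mixed-effects modelling for repeated measures in general terms.

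Section 18.1 tells participants that they are "free to refuse to answer any questions that they do not feel comfortable answering". The stated endpoints in section 3.1 are PAHSS and EmPHasis-10, not the module ratings.

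**The concern.** Asking a participant to finish an overdue PHQ-9 or EmPHasis-10 is ordinary practice and does little harm within a window. A before/after-module rating is different, because its meaning depends on the moment of entry. A before-session value given days later comes from someone who has already done the session, and an after-session value given days later is a memory of how the session felt.

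The chase rule does not separate the two kinds of data. Sections 12, 19 and 22 contain no exemption for module ratings, no entry window, no time-stamp or late-entry flag, and no analysis that leaves late entries out. Section 22.3, written about withdrawals, says the pre-post comparison will use all available data, so it does not screen late entries either. Recalled values would therefore be analysed as if they were momentary.

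The short-term part of Hypothesis 2 is at stake. Module ratings exist only where a module is used, so the waitlist group gives no parallel series in which the same recall error could cancel.

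**Working it through.** **Plan figures.** The documents give no figure for late entries or recall error, so there is none to reproduce on that point. The nearest is practice time in section 13.2: 56 days x 20 min = 1,120 min, and 1,120 / 60 = 18.7 hours, as stated. The enrolment figure also reproduces (16 / (1 - 0.20) = 20, section 5.1), but nothing here depends on it.

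**1. Which data the rule covers.** The opening sentence names the M-App and REDCap. The check and the remedy follow in the same paragraph and name no narrower set. The wording of the check mentions survey completion, which could point mainly to the questionnaires, but it also covers data entry and missing data without limit.

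**2. How many module ratings are scheduled.** Ratings per participant = module days x 4 symptoms x 2 occasions, at one module per day.
- Table 1, self-guided days: 6 x 8 weeks = 48, and 48 x 4 x 2 = 384.
- Section 13.2: 56 days, and 56 x 4 x 2 = 448.
- Near the feasibility threshold in section 2.1 (more than 2 practices a week): 2 x 8 = 16 sessions, and 16 x 4 x 2 = 128.

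These are totals. Only ratings that are missing and then chased are exposed.

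**3. How old a chased rating is.** With a weekly check, a gap is about 0 to 7 days old when found. If gaps are spread evenly over the week, the mean is 3 days (counting 0 to 6) or 4 days (counting 1 to 7). The participant's response time is added to that.

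**4. Effect on the mean change.** Let D be the true mean before/after change, f the share of pairs completed late, and b the mean shift in a recalled change (positive = more apparent relief). If D is the same in on-time and late pairs, then

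observed mean = (1 - f) x D + f x (D + b) = D + f x b, so bias = f x b.

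Both f and b are assumptions. Bias in points on the 1-10 scale:

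| f | b = -1 | b = 0 | b = +1 | b = +2 |
|---|---|---|---|---|
| 5% | -0.05 | 0 | 0.05 | 0.10 |
| 10% | -0.10 | 0 | 0.10 | 0.20 |
| 20% | -0.20 | 0 | 0.20 | 0.40 |
| 30% | -0.30 | 0 | 0.30 | 0.60 |

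The sign follows b. The documents fix neither f nor b.

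**The case against.** The strongest reply is that no section says module ratings will be filled in afterwards. The check can be read as aimed mainly at the scheduled questionnaires. Required fields and prompts should also catch most gaps while the participant is in the App. If the before-rating must be entered to open the module, a skipped module leaves no pair to reconstruct, and the likely gap is only the after-rating. The pre-analysis review by two researchers is a further partial check.

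Much of this stands. The safeguards reduce the problem, but they do not remove it. A prompt cannot obtain an after-rating once the App has been closed, the App's layout is not described, and the protocol expects residual gaps because it plans a chase. The two-researcher review has no rule for late entries and, without time stamps, may be unable to see them.

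A reader might also infer that section 19.3 contradicts the right to refuse in section 18.1. The text is softer than that: the system reminds and the coordinator asks. Whether a required field blocks progress is not stated. What remains is an omission. Refused answers, and items left when a distressed participant is told to turn away from the survey (sections 21.3 and 23.1), are legitimate gaps, and section 19.3 does not exempt them from follow-up.

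**Conclusion.** The point holds as a defect in a stated rule. As written, section 19.3 allows before/after-module ratings to be completed up to a week or more late and then analysed unmarked in the short-term comparison. It does not hold as a demonstrated bias.

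The documents do not support three stronger inferences:
- **That App ratings will in fact be completed late.** The rule permits it, but nothing shows that it occurs.
- **That the error inflates relief.** Participants know they are using the programme, so a lean toward improvement is plausible, but no section establishes it, and a negative recall shift reverses the sign.
- **That all 384 to 448 ratings are exposed.** That is the full schedule under daily practice.

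The possible bias is f x b. It runs from -0.30 to +0.60 points over the assumed ranges (f from 5% to 30%, b from -1 to +2) and is zero if recall is accurate on average. It rests on equal true change in on-time and late pairs.

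Severity is minor to moderate, because the stated endpoints are PAHSS and EmPHasis-10 and the module ratings serve only the short-term part of Hypothesis 2 in a pilot. Confidence is moderate.

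**What to change.** In section 19.3:
- Limit the follow-up request to the scheduled questionnaires (PAHSS, EmPHasis-10, PHQ-9, CAMS-R, SUS), within a stated window.
- State that module ratings not entered at the session stay missing and are not requested later.
- State that answers refused under section 18.1 are coded missing and not chased.

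In section 19.1:
- Where entry times are recorded, exclude late module ratings from the main short-term analysis and include them in a sensitivity analysis.
- Report the share of module ratings that are missing or late.
- Analyse module ratings with the mixed-effects model already named, or with each participant's mean before-after difference. Standard repeated-measures ANOVA drops incomplete cases, which could remove participants from a sample of 20, so the sentence assigning App impact to paired t-test and ANOVA needs to change as well.

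**Cost.** The change takes a few sentences and alters no sample-size figure. The downside is more missing module ratings. The mixed model can use unbalanced data, but it assumes the gaps are unrelated to the unseen ratings given those observed, which is a further reason to report how many are missing. Section 11.1 says enrolment has ended, so App settings may no longer be changeable. The analysis and reporting rules can still be adopted before analysis, but late entries can be identified only if entry times were logged.
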